2. OBJECTIVES

The aim of this project is to find out if the overuse of antibiotics in children with acute respiratory symptoms can be reduced by effectively identifying children at increased risk of infections who require antibiotic therapy and children who will not benefit from antibiotics. This is done by implementing CRP POCT at the primary healthcare level.

Hypotheses:

Supplying CRP POCT equipment to primary healthcare providers will help them identify the majority of children who suffer from viral infections and assist in withholding antibiotic treatment when no benefit can be expected and will help identify the severely sick children in need of urgent referral, thus lowering unnecessary use of antibiotics and improving primary care management by studying supplying supportive medication for those not in need of antibiotics.

It will be an individually randomised clinical trial where CRP POCT is supplied to approximately 14 healthcare centres. All children up to 12 years with respiratory symptoms have basic clinical data recorded as well as data needed to classify according to WHO IMCI pneumonia diagnostic criteria. CRP POCT is used at intervention sites and CRP results, diagnosis, and treatment is recorded. Follow-up phone calls will be made 3, 7 and 14 days after the health centre visit to record recovery, antibiotics use, hospitalisation and vital status of the participating children.

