7. METHODS

7.1 Study parameters/endpoints

The primary outcome of the randomised trial is antibiotic prescription within 14 days from the index consultation, measured as proportion of children in each study group who receive an antibiotic (superiority analysis).

However, any reduction in antibiotic use must be balanced without any compromise to patient safety and the study will therefore include two primary outcomes. The second primary study outcome is patient safety measured as the number of days until recovery (non-inferiority analysis).

Secondary outcomes include other treatment, antibiotics given at index consultation, re-consultations, admissions and vital status.

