Follow-up with Phone Calls

There will be no scheduled follow-up visit at the health clinic required by the study. Parents/caregivers will be phoned 3, 7 and 14 days after the index consultation to record outcomes. Phone calls will be blinded and performed by another AI (see appendix D):

- Number of symptomatic days after the consultation;
- Duration of specific symptoms;
- Return to school/work and usual activities;
- Additional contacts with HCWs;
- Any medicine bought over-the-counter or prescribed by other HCWs including the name of the drug(s);
- Additional diagnostic testing, including SARS-CoV-2 and outcomes;
- Complications (hospitalisation -days in hospital, ICU, medication/oxygen/ventilation received there-, pneumonia, death);
- Infections in their households;
- General well-being;
- Diarrhea

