7.14 Primary study outcomes

The primary study outcome is the proportion of included children in each study arm that are prescribed an antibiotic within 14 days from the index consultation (superiority analysis).

However, any reduction in antibiotic use must be balanced without any compromise to patient safety and the study will therefore include two primary outcomes. The second primary study outcome is patient safety measured as the number of days until recovery (non-inferiority analysis).

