8.4 Benefits and risks assessment, group relatedness

For the children being managed at participating health centres during the intervention period, the study adds a finger prick and, for some, a tracheal swab, which does give some discomfort for the child. On the other hand, it is the intention that the improved diagnosis will lead to better treatment for the child's condition. There is a slight risk that a child has a severe infection with eg. a short prodrome before presenting to the clinician leading to a CRP that is not yet elevated, and if the CRP levels are followed strictly that such a child is not treated with antibiotics. To counter this, part of the training given with the CRP POCT intervention will address such issues and highlight that if the clinician is worried for the child despite a low CRP count, antibiotic therapy should be started. It will also be emphasized that if in doubt, the clinician should re-evaluate the child eg. the next day or what is clinically meaningful. Previous studies very similar to this have shown to be safe for participants.

Sample analyses will become available weeks after the samples were taken, and thereby don't and can't influence patient care or management. Upon request, the national coordinator can supply the sample results to the health clinics after full data analysis, if participants want to inquire their results.

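### The follow-up call item on medicines is narrower than the 14-day antibiotic outcome and may miss an antibiotic started later by the index health worker

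*Combined protocol and SAP*

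**What the plan says.** Section 7.1 states: "The primary outcome of the randomised trial is antibiotic prescription within 14 days from the index consultation". Section 7.14 repeats this without limiting who prescribes. Antibiotics at the index consultation are a separate secondary outcome (7.15), so the 14-day outcome adds information only through later starts.

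Index prescribing is recorded in the CRF (7.5). No clinic follow-up visit is scheduled, and later events come from caregiver calls on days 3, 7 and 14. The call list in 7.5 has one outpatient medicine item: "Any medicine bought over-the-counter or prescribed by other HCWs including the name of the drug(s". It also lists "Additional contacts with HCWs" and, under complications, medication received in hospital.

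Section 2 is broader. There the calls are made "to record recovery, antibiotics use, hospitalisation and vital status of the participating children".

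Later contacts are foreseen. Section 8.4 says the CRP training will stress that "if in doubt, the clinician should re-evaluate the child eg. the next day or what is clinically meaningful", and section 7.21 analyses both planned and unplanned reconsultations.

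**The concern.** Only children who leave the index visit without an antibiotic can change their status on this outcome later. If the index health worker prescribes at a second contact and the call asks only about other prescribers and purchases, the child stays classified as having had no antibiotic. Delayed prescribing is one way an early reduction could be partly undone, so its capture matters for the first primary outcome.

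The weighting in section 7.20 would not help. It addresses missing outcomes and loss to follow-up, whereas an event that was never asked about enters the data as a completed negative.

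**Working it through.** **Coverage of the 14-day window, by source of the antibiotic**

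| Source | Where the plan records it |
|---|---|
| Index consultation | CRF (7.5) |
| Bought over the counter | Call item on medicines (7.5) |
| Another health worker, outpatient | Call item on medicines (7.5) |
| Hospital | Call item on complications (7.5) |
| Index health worker, later outpatient contact | No listed item names it; the contacts item mentions no treatment |

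**The plan's own figure.** Inputs from 7.16: 55% against 45%, 90% power, significance level 0.05 (two-sided reproduces the result). With the pooled formula, n per arm = [1.96 × √(2 × 0.5 × 0.5) + 1.282 × √(0.55 × 0.45 + 0.45 × 0.55)]² / 0.10² ≈ 523.3, rounded up to 524, or 1048 in total against the stated 1046. Power at 523 per arm is 90.0%. The sample size is not in dispute.

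**Size of a spurious difference.** Let u be the proportion leaving the index visit without an antibiotic, r the share of those children later started on one by the same worker, and m the fraction of such starts that the calls fail to record. The spurious difference in favour of CRP is m × (u_CRP × r_CRP − u_control × r_control).

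The documents give none of these quantities. Assume u = 50% in the CRP arm and 45% in the control arm (the latter treats the plan's 55% as an index rate), with m = 1, the worst case.

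| r CRP | r control | Calculation | Spurious points |
|---|---|---|---|
| 5% | 5% | 0.50 × 0.05 − 0.45 × 0.05 | 0.25 |
| 10% | 10% | 0.50 × 0.10 − 0.45 × 0.10 | 0.5 |
| 5% | 3% | 0.50 × 0.05 − 0.45 × 0.03 | 1.15 |
| 10% | 4% | 0.50 × 0.10 − 0.45 × 0.04 | 3.2 |
| 15% | 5% | 0.50 × 0.15 − 0.45 × 0.05 | 5.25 |
| 5% | 10% | 0.50 × 0.05 − 0.45 × 0.10 | −2.0 |

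If the calls pick up half of these starts (m = 0.5), every figure halves. The sign reverses once the control rate exceeds 0.50 / 0.45 = 1.11 times the CRP rate.

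**Equal rates with the planned contrast at index.** With index rates of 55% and 45%, the true 14-day difference is 10 × (1 − r) points while 10 is observed. For r = 5%, 10% and 20% the truth is 9.5, 9.0 and 8.0, an overstatement of 0.5, 1.0 and 2.0 points. With equal rates the gap scales a real effect. It creates none where there is no true difference.

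**False superiority claims.** These need unequal missed shares. Suppose the true 14-day proportion is 55% in both arms, with 523 per arm, 2% of all control children missed, and 1, 2, 3 or 5 points more missed in the CRP arm. For 3 points, the observed proportions are 53% and 50%, SE = √[(0.53 × 0.47 + 0.50 × 0.50) / 523] = 0.0309, and z = 0.03 / 0.0309 = 0.97. The chance of a two-sided significant result is about 16%. For 1, 2 and 5 points it is about 6%, 10% and 37%, against a nominal 5%.

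**The case against.** The strongest reply is that the list in 7.5 is a summary and the instrument is the phone questionnaire, which the documents list by title only. Section 2 describes unrestricted recording of antibiotic use. Section 7.21 analyses antivirals that were prescribed or bought over the counter, with no restriction to other prescribers, and that analysis needs the same follow-up medicine data. The word restricting prescribers may therefore be loose drafting. A question about further contacts would also tend to prompt a report of what was given. This stands: the documents support saying that such an antibiotic may be missed, not that it is.

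A reader might also infer that the gap is bound to flatter the CRP arm because that arm is trained to re-evaluate. The documents do not support this. Health workers are trained, not arms. Randomisation is by child, so the same trained workers can see children from both arms and nothing confines re-evaluation to one of them. What remains is the weaker argument that, if CRP lowers index prescribing, more CRP children are exposed to an unrecorded late start.

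Nor do the documents show that the second contact will usually be with the same worker. Section 7.3 describes FMCs and FPGs with several kinds of staff, and FOPs that refer to an FPG when a family doctor is needed. A prescription by a different worker is captured even on the literal reading.

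**Conclusion.** The concern holds as an inconsistency in how the first primary outcome is ascertained. The item in 7.5 is narrower than the outcome in 7.1 and 7.14 and than the statement in section 2, and the event left out is foreseeable from 7.21 and 8.4.

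On assumed rates with complete non-capture, the spurious difference runs from 0.25 to 0.5 points with equal late-start rates to about 3 to 5 points when the CRP rate is 2.5 to 3 times the control rate, against a targeted 10 points. It is negative if the control rate is sufficiently higher. The larger values, and the false-claim chances of 16% and 37%, depend on between-arm differences that no figure in the documents supports.

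It would also go too far to say that the 14-day outcome collapses into an index-visit outcome, because purchases, other prescribers and hospital medication are all listed. This should be fixed; confidence is moderate because the questionnaire cannot be checked.

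**What to change.** Check the phone questionnaire first. If it already asks about antibiotics from every source, correcting the list in 7.5 is enough. Otherwise reword the item in both places along these lines: any antibiotic or other medicine started since the index consultation, from any source, including the index HCW at a later contact, another HCW, a hospital, a pharmacy or a home supply, with drug name, start date and source.

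Align sections 2 and 7.5 with the questionnaire. Count antibiotics within 14 days according to the 7.14 definition. State whether over-the-counter antibiotics count, since 7.14 speaks of prescription while 7.1 and 7.12 also speak of receipt; the source field makes either choice workable. Tabulate antibiotics first started after the index visit by arm, so that readers can see how much of any index difference persists.

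The cost is one reworded question and a few seconds more per call, with no extra calls, staff or children. It should be done before calls begin, because unasked events cannot be recovered reliably afterwards.

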7.6 Withdrawal of individual participants

Participants can leave the study at any time for any reason if they wish to do so without any consequences. The investigator can decide to withdraw a subject from the study for urgent medical reasons. If any subjects are withdrawn, the reason(s) will be recorded in the CRF.

COORDINATE

7.7 Follow-up of subjects withdrawn from study

The phone numbers of the parents/caregivers of the withdrawn or abandoned participants, if they wish, will be recorded and later called to find out the child's condition. The reasons for the refusal will also be recorded in a special section in the CRF.

7.8 Premature termination of the study and interim analysis

Since we are planning to include all subjects within two to three months, we do not plan to make an interim analysis. If the inclusion period will be longer than 3 months we will do an interim analysis or when 500 participants are included whichever ever comes first. The interim analysis will assess our primary outcome, safety outcome and adverse events. The PI will present the results of interim analysis to the Data Safety Monitoring Board (DSMB) / Safety Committee (see section 7.11).

SAFETY REPORTING

7.9 Temporary halt for reasons of subject safety

The study maybe halted for various reasons such as an urgent safety measures, further to a serious breach, serious sickness of researcher. A temporary halt applies when the suspension is imposed on all sites; suspension of the study at a single site due to logistical reasons is not considered a temporary halt.

The decision on whether a temporary halt should be imposed on a study will ultimately be a steering committee decision (and the decision-making process should be evidenced on file).

7.10 AEs, SAEs and SUSARs

7.10.1 Adverse events (AEs)

Adverse events may include the following:

- Allergic reaction to an antibiotic or any other drug during treatment (skin rash, lacrimation, flushing)
- Individual intolerance to an antibiotic or any other drug.
- Positive a rapid diagnostic test for SARS-CoV-2

7.10.2 Serious adverse events (SAEs)

As part of the study, we will collect the following outcomes at day 3, 7 and 14:

- Death
- Inpatient hospitalisation

SAE data will also be recorded in the CRF.

7.11 Data Safety Monitoring Board (DSMB) / Safety Committee

If need be a Data Safety Monitoring Board or Steering/Safety Committee will be activated and interim analysis including SAE will be presented and discussed. The primary responsibilities of the DSMB are to 1) periodically review and evaluate the accumulated study data for participant safety, study conduct and progress, and, when appropriate, efficacy, and 2) make recommendations to Principal Investigator concerning the continuation, modification, or

COORDINATE

termination of the trial. The DSMB considers study-specific data as well as relevant background knowledge about the disease, test agent, or patient population under study.

Items reviewed by the DSMB include: Interim/cumulative data for evidence of study-related adverse events; Interim/cumulative data for evidence of efficacy according to pre-established statistical guidelines, if appropriate; Data quality, completeness, and timeliness; Performance of individual centres; Adequacy of compliance with goals for recruitment and retention, including those related to the participation of women and minorities; Adherence to the protocol; Factors that might affect the study outcome or compromise the confidentiality of the trial data (such as protocol violations, unmasking, etc.);

The Data Safety Monitoring Board (DSMB) will consist of PI, coordinators from Denmark and Kyrgyz Republic and [name] (paediatrician).

STATISTICAL ANALYSIS PLAN

7.12 General principles

This study is designed as an RCT to test effectiveness of CRP POCT in lowering prescription of antibiotics to children from 6 month to 12 years of age in 14 primary health clinics in Kyrgyzstan presenting with acute respiratory tract infection (see protocol for inclusion criteria) without compromising patient safety. The children will be randomised into two groups: in the intervention group CRP POCT will be measured and used to guide clinical decision-making regarding antibiotic use, in the control group standard care will be performed without CRP measurement. The primary outcome is the proportion of children receiving antibiotics within 14 days from the index consultation in each study arm. The main statistical analysis will follow an intention to treat (ITT) principle, in which all enrolled children will be analysed in the groups they are randomised to. Safety outcomes as well as other secondary outcomes will be assessed as described in 1.2.

The statistical analysis will be performed after data from the last follow up has been entered. Analysis will be performed by the investigators of the study using SAS statistical software. Data will be stored in REDcap.

7.13 Randomisation

The children will be randomised into two groups using the online randomisation tool 'Sealed Envelope' (www.sealedenvelope.com). Randomisation will be stratified by male/female as well as age<5 years and age>5 years.

7.14 Primary study outcomes

The primary study outcome is the proportion of included children in each study arm that are prescribed an antibiotic within 14 days from the index consultation (superiority analysis).

However, any reduction in antibiotic use must be balanced without any compromise to patient safety and the study will therefore include two primary outcomes. The second primary study outcome is patient safety measured as the number of days until recovery (non-inferiority analysis).

7.15 Secondary study parameters/outcomes

- Antibiotics prescribed at the index consultation

COORDINATE

- Antiviral treatment at follow up
- Reconsultation within 14 days from index consultation
- Hospital referral at index consultation
- Hospital admission at follow up
- Mortality

7.16 Power calculation

As the study employs a combined superiority and non-inferiority approach based on the two related primary study outcomes; we provide two power calculations and opt for the conservative number of participants to ensure the adequate sample size for answering both primary outcomes. Power calculations are performed using sample size calculators provided by Sealed Envelope™.

Superiority power calculations show that for a power of 90% to detect a 10% reduction in antibiotic use (from 55% to 45% based on previous pilot registrations in the area) at a statistical significance level of 0.05 a total of 1046 children, 523 in each arm are necessary.

In our non-inferiority power calculation, we apply a margin of non-inferiority of one day (24 hours), i.e. the intervention arm is allowed to have a mean time to recovery that is one day longer than the mean recovery time in the control arm without being deemed inferior. The duration of acute respiratory tract infection in children is approximately 7 days with a standard deviation of 5 days. Hence, for a power of 90% and a statistical significance level of 0.05 a total of 858 children are needed.

To be able to assess both outcomes we will opt for the conservative measure, e.g. the superiority measure.

With an expected dropout rate of 15% we aim to include 1204 children in total, 602 in each arm. This is deemed achievable with the available resources. We expect to be able to include a sufficient number of patients in approximately three months. Each clinic has a patient flow of approximately 10 – 25 children per week. With 10 clinics, the weekly flow of potential participants is 100 – 250 even if only less than 1 in 2 patients are enrolled; we will still keep this schedule.

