Overuse of antibiotics globally is leading to increasing rates of antibiotic resistance and may lead to a 'post-antibiotic' era. Case fatality rates for pneumonia in children remain high in Central Asia and there is a lack of knowledge of which viruses and bacteria cause the disease. Antibiotic resistance patterns of common bacteria remain largely unknown in Central Asia which makes it challenging for clinicians to choose the right antibiotic to treat children with suspected bacterial pneumonia and sometimes healthcare workers overuse an antibacterial therapy even when the child does not need it.

Randomised trials of using CRP point of care test (POCT) to guide antibiotic prescription for respiratory tract infections has been successful in lowering unnecessary antibiotic prescriptions in adults in high income countries but left a small concern for safety in the form of possibly slightly increased risk of hospitalisation in the CRP group.

Objective: This study seeks to gain evidence on whether use of C-reactive protein point-of-care test can safely decrease prescription of antibiotics for children under 12 with acute respiratory symptoms in primary level healthcare centres in Kyrgyzstan.

Study design: Multicentre, open-label, individual randomised controlled clinical trial with 14 days blinded follow-up in rural Chui and Naryn regions of Kyrgyz Republic. Healthcare workers from ten selected healthcare centres will be trained in the CRP POCT and in interpreting the results in the field.

Study population: Children aged from 6 month to 12 years attending the primary level healthcare centres during normal business hours with acute respiratory symptoms.

Main study parameters: The proportion of patients in the two groups prescribed an antibiotic within 14 days of index consultation; length of disease, antibiotics given at index consultation, admissions and vital status.

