4.2 Inclusion criteria

Inclusion criteria is:

- Between 6 month and 12 years of age;
- Parents/caregivers of a child are able and willing to comply with all study requirements;
- Parents/caregivers of a child is able and willing to give Informed Consent;
- Having at least one of the following focal symptoms lasting for less than 2 weeks:
 - Cough;
 - Fast/difficult breathing;
 - Sore throat;
 - Shortness of breath;
 - Wheezing

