When the patient consults at the healthcare centres, explanation of the study, provision of study-related information, patient information sheet and IC will be performed at the practice. All study personnel will be trained by the national network facilitator or Principal Investigator (PI), detailing no less than: the exact nature of the study, implications and constraints of the study, and risks and benefits of participation. The study will provide a patient information sheet (appendix D) that includes all necessary information available in the official national language. 10 minutes will be given to the parents/caregivers to consider the information given to them and to ask any questions they may have about the study to decide whether their child will participate in the study. As participants are not of legal age of consent in their jurisdiction, consent will be provided by their parent/caregiver. It will be clearly stated in the patient information sheet and verbally explained to the participant that they are free to withdraw from the study at any time for any reason without impacting their future care, and with no obligation to provide the reason for withdrawal.

COORDINATE

Study Visit – Inclusion

Patients will be included when they attend the health clinic upon fulfilment of the above-mentioned criteria. During the consultation and upon IC the baseline CRF data will be gathered (see appendix A, for the exact information that will be recorded). The CRF will be completed by the AI; the examination will be carried out by the clinic's HCW.

- Demographic details including: sex, age, co-morbidities, BMI category;
- Duration of CA-ARTI symptoms prior to consulting;
- Presence of specific RTI and general symptoms;
- Overall severity rating (HCW perception);
- Clinical assessments and results of clinical examination (oxygen saturation, respiratory rate, blood pressure, heart rate, body temperature);
- All diagnostic tests performed or ordered;
- Management: antibiotic, antiviral prescription, other (symptomatic) medication prescribed and advised;
- Additional advices: preventive measures for themselves and their family members, time-off, home isolation, hygienic measures;
- Referral to hospital or public health authority;
- During this visit a swab will be taken see below;
- COVID-19-specific questions;
- Participants randomised to a control group will receive routine care. Participants randomised to the CRP group will take the CRP test

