7.22 Adjustment for baseline variables

The analyses of the outcomes will be adjusted for the stratification variables – age and sex – so as to boost the power of the analyses. Additionally, clinical relevant variables such as respiratory frequency, fever and other severity markers will be included.

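### The recovery co-primary has no stated time zero; naming prior symptom duration as a covariate in 7.22 makes the arm difference independent of it and gains precision at no cost

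*Combined protocol and SAP*

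**What the plan says.** Sections 7.1 and 7.14 give the safety co-primary in the same words: "The second primary study outcome is patient safety measured as the number of days until recovery (non-inferiority analysis". Neither gives a starting point, whereas the antibiotic co-primary in the same sections is anchored to the index consultation. Section 7.19 models the same outcome with a covariate-adjusted generalised linear model, states no link, and adds no time zero.

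Other places describe illness duration differently:

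- The Summary lists among the main study parameters "length of disease, antibiotics given at index consultation, admissions and vital status".
- The follow-up calls in 7.5 collect "Number of symptomatic days after the consultation" and, separately, "Duration of specific symptoms", the latter with no origin stated.
- The inclusion visit in 7.5 records "Duration of CA-ARTI symptoms prior to consulting".
- Section 4.2 admits children with "at least one of the following focal symptoms lasting for less than 2 weeks", so the time already ill at entry can vary a good deal.
- Section 7.16 takes its planning values from this statement: "The duration of acute respiratory tract infection in children is approximately 7 days with a standard deviation of 5 days". It sets the margin as a one-day difference between the arms in mean recovery time.

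On adjustment, 7.22 names age and sex and then says that "clinical relevant variables such as respiratory frequency, fever and other severity markers will be included". Symptom duration before the visit is not named.

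**The concern.** Because time ill before the visit is recorded separately, two versions of the outcome can be built from the same records: days from onset and days from consultation. Nothing in the plan expressly fixes which one is analysed. The trial is open-label and 7.12 has its own investigators analyse it after the last follow-up data are entered, so a choice on a non-inferiority co-primary should not be left until then.

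The planning SD is stated for the duration of the infection, while the calls count from the visit. The reader cannot tell whether 5 days describes the outcome to be tested. Prior symptom duration is also a plausible predictor of how long a child remains ill, and leaving it unnamed in 7.22 may forgo precision that is already available.

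**Working it through.** **Inputs.** From 7.16: margin 1 day, SD 5 days, power 90%, level 0.05 (sidedness not stated), total 858, enrolment 1204, dropout 15%. Evaluable per arm: 1204 × 0.85 / 2 = 511.7. Assumed, because the documents give neither: an SD of prior symptom duration of 2 to 4 days, and a correlation r of 0.2 to 0.4 between prior duration and the outcome.

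**1. The plan's own figure.** n per arm = 2 × SD² × (z(1−α) + z(0.90))² / margin².

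- One-sided α = 0.05: 2 × 25 × (1.645 + 1.282)² = 428.2, so 429 per arm and 858 in total. This matches.
- One-sided α = 0.025: 2 × 25 × (1.960 + 1.282)² = 525.4, so 526 per arm and 1052 in total. This does not match.

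So 858 rests on one-sided 0.05. The 95% interval in 7.19, if two-sided, corresponds to one-sided 0.025. That difference is a separate matter; both levels are shown where it counts.

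**2. Direction of any error in the SD.** Let P be days ill before the visit, D days ill after it, and W = P + D. Then Var(W) = Var(P) + Var(D) + 2Cov(P, D). If the SD of 5 belongs to W and P and D are uncorrelated, SD(D) = √(25 − SD(P)²):

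- SD(P) = 2: SD(D) = 4.58, total N 720 at one-sided 0.05
- SD(P) = 3: SD(D) = 4.00, N 550
- SD(P) = 4: SD(D) = 3.00, N 310

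A positive correlation lowers SD(D) further. A negative one can raise it slightly: with SD(P) = 2 and correlation −0.3, SD(D) = 5.22 and N = 936 at one-sided 0.05 (1146 at 0.025).

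**3. The margin.** P is fixed before randomisation, so its expected value is the same in both arms. The difference between arms in mean W therefore equals the difference in mean D, and one day means the same from either origin.

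**4. What the covariate does to the origin.** Write the identity-link model for days after consultation as E(D) = a + b × arm + c × P + other terms. Adding P to both sides gives E(W) = a + b × arm + (c + 1) × P + the same other terms. The coefficient b, its standard error and its confidence interval are identical; only the coefficient of P changes. This needs P entered linearly in days. It does not hold under, for example, a log link.

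**5. Precision.** Taking 5 as the SD of the analysed outcome before adjustment, the residual SD is 5√(1 − r²) and the equivalent gain in sample size is 1/(1 − r²). Power = Φ(1 / (SD × √(2/511.7)) − z(1−α)), with √(2/511.7) = 0.0625. At one-sided 0.025:

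| r | residual SD | equivalent extra children | power |
|---|---|---|---|
| 0 | 5.00 | 0% | 89.2% |
| 0.2 | 4.90 | 4% | 90.4% |
| 0.3 | 4.77 | 10% | 91.8% |
| 0.4 | 4.58 | 19% | 93.7% |

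At the plan's one-sided 0.05, the same formula gives 94% without adjustment and about 95 to 97% with it.

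**The case against.** The documents already lean towards the consultation as time zero. The calls are timed from the index visit, one call item counts symptomatic days from it, prior duration is a separate baseline item, and no section proposes counting recovery from onset. The Summary entry and the call items are never expressly labelled as the co-primary. The phone questionnaire, which might settle the wording, is listed only by title. The covariate list in 7.22 is open-ended, so prior duration is not excluded. All of this stands: a sensible analyst would probably count from the visit, and the missing statement is a matter of detail.

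Three stronger readings are tempting, and the documents do not support them.

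- A reader might add the variance of prior duration to the SD of 5, reach 5.4 to 6.4 days, and conclude that power falls to 84–70%. That treats 5 as the SD after consultation while counting the outcome from onset. Section 7.16 describes the duration of the infection, most naturally the whole illness. On that reading, counting from onset leaves the SD at 5 and counting from consultation probably lowers it.
- A reader might infer that the margin was set on a different scale from the outcome. Step 3 shows that it does not depend on the origin.
- A reader might object that one day is a larger share of the illness remaining after the visit. Section 7.16 states the margin in absolute terms and claims no share, and the documents give no mean for the remaining illness.

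**Conclusion.** The gap is real but small. Time zero is unstated for a co-primary outcome, and its planning SD is not tied to the quantity the calls record. No loss of power is shown: if 5 days is the whole-illness SD, the likely error is conservative. The reading of 5 as whole-illness is natural but inferred, and a negative correlation between prior and remaining duration would weaken the conclusion slightly.

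What remains worth doing is the covariate. Its benefit in making the arm difference independent of the origin is algebraic, given an identity link and a linear term. Its precision gain of about 4 to 19% in equivalent sample size rests on the assumed correlation of 0.2 to 0.4, which the documents neither support nor contradict. This is a free improvement, and nothing here suggests that the non-inferiority analysis would fail without it.

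**What to change.** 1. In 7.22, pre-specify symptom duration before consultation, in days and as a linear term, as a covariate in the recovery model. In 7.19, state that this model uses an identity link.
2. In 7.1, 7.14 and 7.19, state that days to recovery are counted from the index consultation as day 0.
3. In 7.16, say whether the mean of 7 and SD of 5 describe the whole illness or the days after consultation.

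The cost is a few lines of SAP wording and one variable already on the case report form. No new data, no extra children and no change to the margin are needed.
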